6.2 IMPORTANT PROTOCOL DEVIATIONS

Data discrepancies and deviations from the CTP will be identified for all treated subjects.

Categories which are considered to be iPDS in this trial were defined in the integrated quality and risk management plan (IQRMP) prior to trial initiation. The list of iPD categories was transferred into the iPD specification file (due to changes in the SOP) (3). Within this transfer some minor adaptations were done to comply with new naming conventions and categorisations.

Consistency check listings (for identification of deviations of time windows) and a list of protocol deviations (e.g. deviations in drug administration, in blood sampling times, etc.) will be provided to be discussed at the Report Planning Meeting (RPM). At this meeting, all manual deviations identified at the sites by the CRAs and deviations too complex to program will be reviewed by the trial team to decide which are considered important. For definition of important protocol deviations (iPD), and for the process of identification of these, refer to the Boehringer Ingelheim (BI) SOP "Identify and Manage Important Protocol Deviations (iPD)" (2).

iPDs will be identified no later than in the Report Planning Meeting. If any iPDS are identified, they are to be summarised into categories and will be captured in the decision log and in the iPD specification file (3). The iPD categories will be updated as needed. The decision on exclusion of subjects from analysis sets will be made after discussion of exceptional cases and implications for analyses.

The iPDS will be listed.

6.3 SUBJECT SETS ANALYSED

Section 7.3 of the CTP: Statistical analyses will be based on the following analysis sets:

- *Treated set (TS): The treated set includes all subjects who were entered and treated with one dose of trial drug. The treated set will be used for safety analyses.*
- *Pharmacokinetic parameter analysis set (PKS): This set includes all subjects from the treated set (TS) who provide at least one pharmacokinetic endpoint that was defined as primary or secondary and was not excluded due to a protocol deviation relevant to the evaluation of pharmacokinetics or due to pharmacokinetic non-evaluability (as specified in the following subsection 'Pharmacokinetics'). Descriptive analyses of pharmacokinetic parameters will be based on the PKS.*

[...]

Plasma, urine and faeces concentration data and parameters of a subject will be included in the statistical pharmacokinetic analyses if they are not flagged for exclusion due to a protocol deviation relevant to the evaluation of pharmacokinetics (to be decided no later than in Report Planning Meeting) or due to pharmacokinetic non-evaluability (as revealed during data analysis, based on the criteria specified below). Exclusion of a subject's data will be documented in the CTR.

Relevant protocol deviations may be

- *Incorrect trial medication taken, i.e. the subject received at least one dose of trial medication the subject was not assigned to*
- *Incorrect dose of trial medication taken*
- *Use of restricted medications*

Plasma and urine concentrations and/ or parameters of a subject will be considered as non-evaluable, if for example

[figure not shown]
- *Missing samples/ concentration data at important phases of pharmacokinetic disposition curve*

Plasma/urine concentration data and parameters of a subject which is flagged for exclusion will be reported with its individual values but will not be included in the statistical analyses.

The descriptive analysis of PK concentrations and endpoints will be based on the ADS ADPC as described in [Section 7](#).

Table 6.3: 1 Subject sets analysed

| Endpoint/data description | Subject set | |
|---|-------------|-----|
| | TS | PKS |
| Primary endpoints | | X |
| Safety parameters (including secondary safety endpoint) | X | |
| Secondary [REDACTED] endpoints | | X |
| Demographic/baseline parameters | X | |
| Important protocol deviations | X | |
| Disposition | X | |

6.5 POOLING OF CENTRES

This section is not applicable, because the study was performed in only one centre.

6.6 HANDLING OF MISSING DATA AND OUTLIERS

Handling of missing data and outliers will be performed as described in the CTP, Section 7.5.

The only exceptions where imputation might be necessary for safety evaluation are AE dates. Missing or incomplete AE dates are imputed according to BI standards (see BI-KMED-BDS-HTG-0035 (4)).

Missing data and outliers of PK data are handled according to BI standards (see BI-KMED-TMCP-MAN-0012 (5) and BI-KMED-TMCP-MAN-0014 (6)).

Missing baseline laboratory values will be imputed by the respective screening values.

6.7 BASELINE, TIME WINDOWS AND CALCULATED VISITS

The baseline value is defined as the last measurement before trial medication administration.

Section 6.1 of the CTP: *Exact times of measurements outside the permitted time windows will be documented. The acceptable time windows for screening and the end of trial examination are provided in the CTP Flow Chart.*

Trial measurements and assessments scheduled to occur 'before' trial medication administration on Day 1 are to be performed and completed within a 3 h-period prior to the trial drug administration.

The acceptable deviation from the scheduled time for vital signs, ECG and laboratory tests will be \pm 30 minutes for the first 4 hours after drug administration and \pm 45 minutes thereafter.

According to the flow chart of the CTP, after day 9 the planned times for admission, discharge, start and end of the urine and faeces collection intervals are approximate. The procedures are to be performed within a time window of +/- 4 hours to the planned time.

Adherence to time windows will be checked via the consistency check listings at the RPM.

Unscheduled measurements of laboratory data and vital signs data will be assumed to be repeat measurements of the most recent scheduled measurement (e.g. for follow-up or confirmation of a particular value). Therefore, unscheduled measurements will be assigned to the planned time point of the previous scheduled measurement.

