7. All stools (for (C-14) BI 1265162 -radioactivity and metabolic profiling) will be collected quantitatively in portions up to 192 hours (sampling intervals of 0-24, 24-48, 48-72, 72-96, 96-120, 120-144, 144-168,168-192 hours) after administration of BI 1265162 (C-14). Thereafter 24-h collections are to be performed on Days 14-16, 21-23, 28-30, and 35-37. A blank sample will be collected before drug administration on Day -2, Day -1 or Day 1 (see [Section 5.3.2.6](#)). Faeces sampling for (C-14) BI 1265162 -radioactivity assessment will be stopped when the release criteria for radioactivity recovery (see [Section 3.1](#)) have been met (earliest stopping on Day 9). “+” means end of last collection interval, start of following collection interval. For details on sample usage, see [Section 5.3.2.6](#).
8. Measurement of haematocrit and potassium, only.
9. AEs and concomitant therapies will be recorded throughout the trial. At 1:05, 2 , 4 , 8, 24, 48, 192h after the infusion, local tolerability will be assessed according to the criteria put down in [Section 2.2.4](#).
10. End-of-trial (EoT) examination to be performed after last discharge from the trial centre, or, if all once-weekly 24-hour sampling periods are needed, after discharge on Day 37. EoT examination includes physical examination, vital signs, ECG, safety laboratory, recording of AEs and concomitant therapies.
11. The planned times for admission, discharge, start and end of the urine and faeces collection intervals are approximate. The procedures are to be performed within a time window of +/- 4 hours to the planned time.
12. Subjects are to collect faeces at home within 24-hour intervals before admission to once-weekly in-house collection intervals. Home collection intervals: Days 14-16, 21-23, 28-30, and 35-37. If faeces are collected in the subsequent in-house collection interval, faeces collected at home will be discarded. If no faeces is collected in the subsequent in-house collection interval (no defecation), faeces collected at home will be used instead for analysis.
13. For definition of the individual subject's end of trial, see [Section 6.2.3](#).
14. Subjects will collect a pre-dose faeces sample at home or at the site in specific containers provided by [REDACTED]

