5.2.6.1.4 Adverse events of special interest

The term adverse events of special interest (AESI) relates to any specific AE that has been identified at the project level as being of particular concern for prospective safety monitoring and safety assessment within this trial, e.g. the potential for AEs based on knowledge from other compounds in the same class. AESIs need to be reported to the sponsor’s Pharmacovigilance Department within the same timeframe that applies to SAEs, see [Section 5.2.6.2.2](#).

Proprietary confidential information © 2020 Boehringer Ingelheim International GmbH or one or more of its affiliated companies

The following are considered as AESIs:

- A confirmed elevation of serum potassium > upper limit of normal (ULN) in non-haemolysed blood.
- Hepatic injury
A hepatic injury is defined by the following alterations of hepatic laboratory parameters:
 - An elevation of AST (aspartate transaminase) and/or ALT (alanine transaminase) ≥ 3 -fold ULN combined with an elevation of total bilirubin ≥ 2 -fold ULN measured in the same blood sample, or
 - Aminotransferase (ALT, and/or AST) elevations ≥ 10 fold ULN

These lab findings constitute a hepatic injury alert and the subjects showing these lab abnormalities need to be followed up according to the 'DILI checklist' provided in the eCD. In case of clinical symptoms of hepatic injury (icterus, unexplained encephalopathy, unexplained coagulopathy, right upper quadrant abdominal pain, etc.) without lab results (ALT, AST, total bilirubin) available, the Investigator should make sure that these parameters are analysed, if necessary in an unscheduled blood test. Should the results meet the criteria of hepatic injury alert, the procedures described in the DILI checklist should be followed.

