7.3.4 Safety analyses

Safety will be analysed based on the assessments described in [Section 2.2.2.2](#). All treated subjects (TS, refer to [Section 7.2](#)) will be included in the safety analysis. Safety analyses will be descriptive in nature and based on BI standards. No hypothesis testing is planned.

For all analyses, the treatment actually administered (= treatment at onset) to the subject will be used (any deviations from the planned treatment will be discussed in the minutes of the Report Planning Meeting).

Treatments will be compared in a descriptive way. Tabulations of frequencies/proportions will be used to evaluate categorical (qualitative) data, and tabulations of descriptive statistics will be used to analyse continuous (quantitative) data.

Measurements (such as vital signs, or laboratory parameters) or AEs will be assigned to treatments (see [Section 4.1](#)) based on the actual treatment at the planned time of the measurement or on the recorded time of AE onset (concept of treatment emergent AEs). Therefore, measurements planned or AEs recorded prior to first intake of trial medication will be assigned to the screening period, those between trial medication intake and discharge from study site (see [Section 1.2.6](#)) will be assigned to the treatment period. Events occurring after discharge from study site but prior to end of trial termination date will be assigned to 'follow-up'. These assignments including the corresponding time intervals will be defined in detail in the TSAP. Note that AEs occurring after the last per protocol contact but entered before final database lock will be reported to Pharmacovigilance only and will not be captured in the trial database.

Additionally, further treatment intervals (analysing treatments) may be defined in the TSAP in order to provide summary statistics for time intervals, such as combined treatments, on-treatment totals, or periods without treatment effects (such as screening and follow-up intervals).

Adverse events will be coded using the Medical Dictionary for Regulatory Activities (MedDRA). Frequency, severity, and causal relationship of AEs will be tabulated by treatment, system organ class, and preferred term. SAEs, AESIs (see [Section 5.2.6.1.4](#)), and other significant AEs (according to ICH E3) will be listed separately.

Previous and concomitant therapies will be presented per treatment group without consideration of time intervals and treatment periods.

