7.8.3 Vital signs

For vital signs (blood pressure and pulse rate), listings including change from baseline will be presented by planned time point based on the last value of the subject at that planned time point (or assigned to that planned time point).

Clinically relevant findings in vital signs will be reported as AEs.

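### SAP 6.7 assigns unscheduled lab and vital-sign values backwards with no dosing boundary, so one taken during or soon after the infusion carries the pre-dose label

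*SAP*

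**What the plan says.** SAP 6.7 sets the premise: "Unscheduled measurements of laboratory data and vital signs data will be assumed to be repeat measurements of the most recent scheduled measurement". It then draws the consequence: "unscheduled measurements will be assigned to the planned time point of the previous scheduled measurement". No time limit is given, and nothing is said about a value taken after administration has begun. The same section defines baseline separately: "The baseline value is defined as the last measurement before trial medication administration".

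SAP 7.8.3 decides which vital-sign value is displayed. The change-from-baseline listing is by planned time point and is "based on the last value of the subject at that planned time point", and values assigned to that time point count as well. SAP 7.8.2 has no such selection rule for labs. It flags out-of-range and possibly clinically significant values in the listings.

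SAP 4 restricts labs and vital signs to listings, for Part 1 only. SAP 7 says that individual values of all subjects are listed.

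**The concern.** The premise suits a prompt confirmatory repeat. It does not suit a reading taken because a subject develops symptoms during the infusion. That reading is new post-dose information, yet the rule files it under the last planned time, which is before dosing.

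Unscheduled values can be foreseen in this trial. The potassium event of special interest in Protocol 5.2.6.1.4 requires a confirmed elevation. For symptoms of hepatic injury without results available, the same section says that "the Investigator should make sure that these parameters are analysed, if necessary in an unscheduled blood test".

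What is at stake is whether a reader of the listings can tell a pre-dose value from a post-dose one. Listings are the only planned lab and vital-sign output, so their time labels have to be right.

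**Working it through.** No power, alpha or sample-size figure is involved. The check applies the SAP rule to the Part 1 schedule.

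**Inputs**

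- Infusion: 0 to 1 h (Protocol synopsis and 4.1.4).
- Vital signs, Flow Chart 1: -2, 4, 12 and 192 h. The extracted table is broken, but Flow Chart 2 shows the same times. A mark at 24 h appears to belong to adverse-event questioning. If it were a vital-sign mark, the pre-dose result below would not change.
- Potassium and haematocrit, Flow Chart 1: -2, 2, 4, 8 and 48 h, with laboratory set B at 192 h. Footnote 8 describes the -2 to 48 h samples as "Measurement of haematocrit and potassium, only".

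**Rule:** label(t) = the largest planned time not later than the actual time t.

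| Actual time of unscheduled value | Lab label | Vital-sign label |
|---|---|---|
| 0.5 h (during infusion) | -2 h | -2 h |
| 1.5 h | -2 h | -2 h |
| 3 h | 2 h | -2 h |
| 5 h | 4 h | 4 h |
| 9 h | 8 h | 4 h |

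**Spans that receive the pre-dose label**

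- Vital signs: 0 to <4 h, which is the 1 h infusion plus 4 - 1 = 3 h after it.
- Potassium and haematocrit: 0 to <2 h, which is the 1 h infusion plus 2 - 1 = 1 h after it.

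These limits are nominal. Protocol 6.1 allows ±30 minutes over the first 4 hours, so the actual end of each span moves with the scheduled measurement. Later unscheduled values can be labelled well before they were taken, for example up to 192 - 12 = 180 h for vital signs, but those labels are still post-dose.

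**What the vital-signs listing would show.** Let P be the scheduled pre-dose reading and U an unscheduled reading at 0.5 h.

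1. Baseline under SAP 6.7 is P, the last reading before administration.
2. The -2 h slot holds both P and U, because U is assigned there.
3. SAP 7.8.3 takes the last of these, which is U.
4. The -2 h row therefore shows U with change U - P. If P stood in that row, the change would be P - P = 0.

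So the pre-dose row would display a post-dose change, and SAP 6.7 and 7.8.3 do not address this. By the same selection rule, an abnormal 4 h reading followed by a normal repeat is represented in the 4 h row by the repeat.

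**Labs.** Steps 1 and 2 apply, but step 3 does not, because SAP 7.8.2 selects no value. Only the label is wrong.

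**The case against.** The best defence is that little depends on these labels. Individual values are listed, no lab or vital-sign summary is planned, and 7 subjects can be read line by line. Clinically relevant findings become adverse events, which Protocol 7.3.4 and SAP 6.1 place by onset time and not by planned time point. Events of special interest are reported within 24 hours (Protocol 5.2.6.2.2) and tabulated (SAP 7.8.1). All of this stands, and it makes the point a small one. It does not make the -2 h label correct. SAP 7 also does not say that the actual time or the displaced reading appears in the SAP 7.8.3 listing.

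A reader might infer more than the documents support:

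- **That repeats overwrite abnormal lab values.** Nothing in SAP 7.8.2 says so. The last-value rule is confined to the vital-signs listing, and choosing the last repeat is in itself an openly stated convention.
- **That baseline is contaminated.** Its definition refers to administration and not to a planned time point, so a post-dose value cannot be baseline.
- **That drug effects are moved into the screening period.** Under Protocol 7.3.4, "measurements planned or AEs recorded prior to first intake of trial medication will be assigned to the screening period", so the carried-back label would fall there on a literal reading. But SAP 6.1 defines phases for adverse events only, and no by-phase lab or vital-sign analysis is planned that could be distorted.
- **That a Day 5 liver panel is filed as Day -1.** This requires the rule to be applied parameter by parameter, which SAP 6.7 does not state. Applied by lab sampling time, the panel would go to 48 h, which is post-dose.

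**Conclusion.** Wrong as written; low priority. Applied literally, SAP 6.7 gives the -2 h label to any unscheduled vital sign at 0 to <4 h and to any unscheduled potassium or haematocrit at 0 to <2 h after the start of the infusion. For vital signs the error reaches a planned output, because the change-from-baseline listing would show the post-dose reading in the pre-dose row. For labs it is a labelling error only.

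No endpoint estimate, baseline value or adverse-event count changes. The conclusion rests on the Flow Chart columns as read from a damaged table. The pre-dose labelling itself needs only that the first scheduled post-dose measurement comes after the infusion starts. The documents do not say how many unscheduled values exist, so the practical effect could be nil.

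**What to change.** In SAP 6.7, state that no measurement taken after the start of administration is assigned to a pre-dose time point. In SAP 6.7 and 7.8.3, list unscheduled post-dose values as unscheduled, at their actual time after dosing, alongside the scheduled value. The vital-signs listing would then show both the scheduled reading and any repeat.

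The cost is a few lines of SAP wording and listing code. No new data are needed, since the existing rule already depends on knowing when each unscheduled value was taken. Basing the change from baseline strictly on the scheduled value, or adding a listing of each subject's highest and lowest post-dose values, would be a matter of preference and is not needed to correct the error.

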7. PLANNED ANALYSIS

Safety analysis (refer to [Section 7.8](#)) will be performed by [REDACTED] and will be presented in Sections 15.1 to 15.4 of the CTR and in Appendix 16.2 and 16.1.13.1.

Descriptive data analysis of PK endpoints and concentrations (including mass balance endpoints) will be performed by the department [REDACTED] at [REDACTED] and will be presented in Section 15.6 of the CTR.

The format of the listings and tables will follow the BI standards (see BI-KMED-BDS-HTG-0045 [\(7\)](#)) with the exception of those generated for PK-calculations following BI standards for PK/PD analysis [\(8\)](#).

The individual values of all subjects will be listed, sorted by treatment group, subject number, visit and actual treatment (if appropriate).

The listings will be included in Appendix 16.2 of the CTR.

For end-of-text tables, the set of summary statistics for non-PK parameters is:

| | |
|--------|---------------------------------|
| N | number non-missing observations |
| Mean | arithmetic mean |
| SD | standard deviation |
| Min | minimum |
| Median | median |
| Max | maximum |

For analyte concentrations, the following descriptive statistics will additionally be calculated:

| | |
|-------|-------------------------------------|
| CV | arithmetic coefficient of variation |
| gMean | geometric mean |
| gCV | geometric coefficient of variation |

For PK parameters, the following descriptive statistics will additionally be calculated:

| | |
|-------|-------------------------------------|
| CV | arithmetic coefficient of variation |
| gMean | geometric mean |
| gCV | geometric coefficient of variation |
| P10 | 10th percentile |
| Q1 | 1st quartile |
| Q3 | 3rd quartile |
| P90 | 90th percentile |

The data format for descriptive statistics of concentrations will be identical to the data format of the respective concentrations. The descriptive statistics of PK parameters will be calculated using the individual values with the number of decimal places as provided by the evaluation program. Then the individual values as well as the descriptive statistics will be reported with three significant digits in the CTR.

Tabulations of frequencies for categorical data will include all possible categories and will display the number of observations in a category, as well as the percentage (%). Percentages will be rounded to one decimal place and will be based on all subjects in the respective subject set whether they have non-missing values or not. The category 'missing' will be displayed only if there are actually missing values.

Exclusion of PK parameters

The ADS ADPP (PK parameters) contains column variables indicating inclusion/exclusion (APEXC) of a PK parameter and an analysis flag comment (APEXCO). All analyses based on the PKS will include parameters if they are not flagged for exclusion that is APEXC is equal to "Included".

Exclusion of PK concentrations

The ADS ADPC (PK concentrations per time-point or per time-interval) contains column variables ACEXC and ACEXCO indicating inclusion/exclusion (ACEXC) of a concentration and an analysis flag comment (ACEXCO). Exclusion of a concentration depends on the analysis flag comment ACEXCO. For example, if ACEXCO is set to 'ALL CALC', the value will be excluded for all types of analyses based on concentrations. If ACEXCO is set to 'DESC STATS' the value will be excluded from descriptive evaluations per planned time point/time interval. If ACEXCO contains the addition 'TIME VIOLATION' or 'TIME DEVIATION' the value can be used for further analyses based on actual times. If ACEXCO is set to 'HALF LIFE', the value will be excluded from half-life calculation [REDACTED] [REDACTED] only; the value is included for all other analyses.

Further details are given in *BI-KMED-TMCP-MAN-0014* "Noncompartmental Pharmacokinetic / Pharmacodynamic Analyses of Clinical Studies" (6) and *BI-KMED-TMCP-MAN-0010*: "Description of Analytical Transfer Files and PK/PD Data Files" (9).

